### **7.4.4 Virology Analysis**

The viral efficacy (viral shedding based on qPCR and cell culture) and characterization of SARS-CoV-2 viral isolate (genotyping) will be analyzed on the ITT set. Actual values and change from baseline for viral shedding, percentage of patients with positive/negative viral shedding, duration (in days) of viral shedding, and AUC of viral levels will be summarized by the cohort of CT-P59 groups and pooling of placebo group at each scheduled visit using descriptive statistics or frequency tables. Mean viral load titer (log values) for each scheduled time point will be plotted. Genotype results will be presented in data listing by the cohort of CT-P59 groups and pooling of placebo group.

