### 3 Investigational Plan

#### 3.1 Study Design

This is a randomized, double-blind, placebo-controlled, parallel group, single ascending dose, Phase 1, pilot study to evaluate the safety, tolerability and virology of CT-P59 in combination with standard of care (SoC), except potential antiviral drugs and/or immune-based therapy under evaluation for treatment of SARS-CoV-2 infection, in patients with mild symptoms of SARS-CoV-2 infection. Approximately 18 patients in 3 cohorts are planned for enrollment and each cohort will consist of 6 patients, 5 of whom will receive CT-P59 and 1 of whom will receive a placebo. In each cohort, patients will be randomized in a 5:1 ratio to receive CT-P59 or placebo.

This study will be started with the lowest dose that will maximize safety and the dose levels will be escalated to the higher doses. The details of dose escalation and stopping criteria is specified in [Section 3.3](#). The overview of the study is presented in [Figure 3-1](#).

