5.5. Definition of Baseline

The baseline value will be considered to be the last non-missing value before the study drug administration. Post-baseline values will be considered to be all measurements collected after the study drug administration.

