9. VIROLOGY ANALYSIS

Virology analysis will be conducted on the ITT set unless otherwise stated.

Virology analysis consists of viral efficacy (viral shedding based on qPCR), characterization of SARS-CoV-2 viral isolate (genotyping) and RT-PCR. Viral shedding (qPCR) and genotype samples will be analyzed at the central laboratory and RT-PCR sample will be analyzed at the local laboratory.

If the patient had RT-PCR result confirming SARS-CoV-2 infection prior to obtaining written informed consent (but no more than 7 days from the onset of symptoms), the result can be allowed. During the Screening Period, only one retest for RT-PCR will be allowed, if study drug can be administered no more than 7 days from onset of symptom based on retest results.

Nasopharyngeal swab samples for virology analysis will be collected and corresponding virology analysis will be performed at the time point specified in [Appendix 1](#) and [Appendix 2](#).

Viral titers will be assessed in log₁₀cp/mL for qPCR. The following [Table 2](#) presents how viral titers will be treated in descriptive summary and AUC calculation, and categorized to Positive or Negative.

Table 2 Handling of Viral Titers (qPCR)

	Treated as	Classified as
Quantitative value	Reported value	Positive
BLQ	LLoQ	Positive
Negative	0	Negative

Abbreviations: qPCR= quantitative polymerase chain reaction; BLQ=below the low limit of quantification; LLoQ=lower limit of quantification. NA= Not Applicable.

Actual results and change from baseline for viral shedding in nasopharyngeal swab specimens (titers) for qPCR will be summarized by treatment groups at each scheduled time point. The number and percentage of patients with positive / negative for qPCR will also be summarized by treatment group and scheduled time point.

Duration (days) of viral shedding in nasopharyngeal swab specimens for qPCR will be calculated as (date/time of post-baseline last positive sample - date/time of study drug administration). Patients with at least one positive sample after baseline will be included in the summary. Duration of viral shedding for qPCR will be summarized by treatment groups using descriptive statistics.

AUC of viral titers for qPCR is calculated from date/time of study drug administration to date/time of last measurable value of patients who have at least one post-baseline result

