(including BLQ and negative values) using linear trapezoidal rule. Viral titer at baseline will be considered as result at study drug administration. AUC of viral titers for qPCR will be summarized by treatment groups using descriptive statistics.

Mean (\pm SD) viral titer of qPCR for each scheduled time point will be plotted by treatment group.

All virology results including qPCR and RT-PCR will be listed for each patient by treatment group and time point respectively.

Genotype results will be listed by treatment group in patients with predose sample with $> 3 \log_{10}$ cp/mL in ITT set. Day 1 (SARS-CoV-2 positive sample) and the last SARS-CoV-2 positive sample in time with $> 3 \log_{10}$ cp/mL will be analyzed. Additional samples were analyzed if SARS-CoV-2 infection symptoms were deteriorated or viral titers were not noticeably reduced.

The first CSR will present viral shedding in nasopharyngeal swab specimens based on qPCR up to Day 7 of each patient displaying descriptive statistics for actual results and change from baseline, and frequency table for categorized results and figure for mean (\pm SD) of viral titer. All virology analysis will be presented in the Final CSR.

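### Viral AUC is summarised by small dose groups with no adjustment for the pre-dose titer it starts from, so a baseline imbalance can hide or mimic a dose effect

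*Protocol*

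**What the plan says.** Protocol section 7.4.4 lists actual values, change from baseline, positive/negative status, duration and AUC of viral levels, all on the ITT set. For the AUC it says "AUC of viral levels will be summarized by the cohort of CT-P59 groups and pooling of placebo group".

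SAP section 9 supplies the mechanics:

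- Time span: "AUC of viral titers for qPCR is calculated from date/time of study drug administration to date/time of last measurable value". Negative and below-quantification results count towards it.
- Starting point: "Viral titer at baseline will be considered as result at study drug administration". SAP section 5.5 defines baseline: "The baseline value will be considered to be the last non-missing value before the study drug administration". The AUC is not baseline-subtracted.
- Coding: SAP Table 2 "presents how viral titers will be treated in descriptive summary and AUC calculation". A result below quantification takes the LLoQ, and Negative takes 0.
- Presentation: "AUC of viral titers for qPCR will be summarized by treatment groups using descriptive statistics". Likewise, "Actual results and change from baseline for viral shedding in nasopharyngeal swab specimens (titers) for qPCR will be summarized by treatment groups".

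Neither document gives a baseline covariate, an estimated group difference or a confidence interval for virology. SAP section 13.1, which lists changes to the planned analysis, does not touch the point. The only regression in the SAP is the power model for PK dose proportionality in section 11.2.

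In each cohort there are six patients, "5 of whom will receive CT-P59 and 1 of whom will receive a placebo". SAP section 5.4 pools placebo, so the groups are 5, 5, 5 and 3. The first report shows qPCR results to Day 7 without the AUC; the AUC appears only in the final report.

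**The concern.** Viral efficacy is the first-listed secondary objective, and virology is in the study title. No test is planned, so readers will judge a dose effect on viral load by eye from group AUC values.

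The AUC depends on where a patient starts. If later titers track the starting titer at all, a group that began higher has a larger AUC with no drug effect. With five patients against three, a chance gap in starting titer can be as large as anything the drug might do. Such a gap could hide a real dose effect or create the look of one.

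The pre-dose titer that would account for much of this is already scheduled on Day 1 for every patient and is not used.

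**Working it through.** The documents state no titer SD, effect size or power for virology, so there is no planned figure to reproduce. The total of 3 × (5 + 1) = 18 patients agrees with the text. Titer, decline and noise values below are assumptions.

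**1. How likely is a baseline gap?** For 5 versus 3 patients the SE of the difference in mean baseline is SD × √(1/5 + 1/3) = 0.730 × SD. For 5 versus 5 it is SD × √(1/5 + 1/5) = 0.632 × SD. Under a normal distribution:

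| Assumed baseline SD (log10) | SE, 5 v 3 | Chance of gap > 1 log10, 5 v 3 | Same, 5 v 5 |
|---|---|---|---|
| 1.0 | 0.73 | 17% | 11% |
| 1.5 | 1.10 | 36% | 29% |
| 2.0 | 1.46 | 49% | 43% |

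**2. What does a gap do with no drug effect?** Protocol Table 6-2 places swabs at 0, 24, 48, 72, 96, 120, 144, 216, 312, 480 and 648 hours. The trapezoid weights sum to 27 days. The time-zero point carries 0.5 day and the later points 26.5 days. Let β be the shift in every later titer per 1 log10 of baseline. Then +1 log10 at baseline moves the AUC by 0.5 + 26.5β and moves change from baseline by β − 1.

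| β | AUC (log10 × days) | Change from baseline (log10) |
|---|---|---|
| 0 | +0.5 | −1.0 |
| 0.5 | +13.75 | −0.5 |
| 0.7 | +19.05 | −0.3 |
| 1.0 | +27.0 | 0 |
| 1.2 | +32.3 | +0.2 |

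The AUC rises for any β ≥ 0, almost entirely through later titers that track the start. Change from baseline moves the other way only when β < 1. Coding Negative as 0 pushes β below 1 once patients clear, because a cleared patient's change is exactly minus the baseline.

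**3. A worked pair.** Take a decline of 0.4 log10/day to zero. The AUC is b²/(2 × 0.4): 49/0.8 = 61.25 for a baseline of 7, and 25/0.8 = 31.25 for a baseline of 5. Change from baseline is the same in both until the lower patient reaches zero, 5/0.4 = 12.5 days after dosing. At Day 7 it is −(6 × 0.4) = −2.4 in both, and at Day 10 it is −(9 × 0.4) = −3.6 in both. At Day 14 it is −5.2 against −5.0, and at Day 28 it is −7 against −5.

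**4. What does adjustment gain for the AUC?** Simulation of 4,000 trials of 18 patients on the Table 6-2 times, assuming mean baseline 6 log10, decline 0.4/day (SD 0.1) independent of baseline, assay noise SD 0.5, values below 1.5 coded 0, and all swabs taken. SE of the 80 mg/kg minus placebo AUC difference, in log10 × days:

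| Baseline SD | Unadjusted | Baseline as covariate | Variance removed |
|---|---|---|---|
| 1.0 | 16.7 | 12.8 | 1 − (12.8/16.7)² = 41% |
| 1.5 | 20.9 | 13.5 | 1 − (13.5/20.9)² = 58% |
| 2.0 | 26.9 | 14.7 | 1 − (14.7/26.9)² = 70% |

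Repeat runs agreed to within about 1 unit. For scale, a 25% faster decline (0.5 instead of 0.4/day) from a baseline of 6 moves the AUC from 36/0.8 = 45 to 36/1.0 = 36, a shift of 9; in simulation it was about 10.

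Residual df are 18 − 4 groups − 1 slope = 13, with a t multiplier of 2.16. The adjusted 95% half-width is therefore about 2.16 × 12.8 = 28 to 2.16 × 14.7 = 32.

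**5. Change from baseline under the same model.** Among no-effect trials with a baseline gap above 1 log10, AUC and change favoured different groups in about 52–53% at Day 7, 65–73% at Day 14 and over 90% at Day 28. Adjusting the Day 7 change gains nothing: the SE goes from 0.72–0.76 to 0.74–0.78. At Day 28 all 18 titers are 0 in 56–75% of trials. Change then equals minus baseline exactly, and the model has no residual variance.

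**The case against.** This is an 18-patient pilot with safety as its primary objective. The plan disclaims hypotheses, and dose escalation rests on safety criteria alone. Descriptive virology is a legitimate choice here. A reader might infer that the groups are formally compared and an error rate is distorted. The documents do not support that: no virology test, contrast or interval is planned.

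A reader might also infer that a baseline gap always drives AUC and change from baseline in opposite directions. It does not. Under the assumed model that is near a coin toss at Day 7 and becomes marked only once many titers sit at 0. It cannot show as a conflict in the first report, which carries no AUC.

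Actual values, mean-titer plots and patient listings are planned, so an imbalance would be visible. Even after adjustment, an interval of about ±28 to ±32 cannot resolve a shift near 10.

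All of this stands, and it lowers the importance of the point. It does not remove it. Seeing an imbalance does not tell the reader how much of an AUC gap it explains, and an adjusted estimate does.

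**Conclusion.** The point holds for viral AUC. The planned summary leaves a known, already scheduled source of variation in the result, in groups where baseline gaps above 1 log10 are plausible. On the assumed values, adjustment removes roughly 40% to 70% of the variance of the 80 mg/kg versus placebo AUC difference.

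The size depends on assumptions. A separate simulation, with decline 0.35/day, assay noise 0.7 and baseline SD 1.5, gave a smaller fall in the SD of the 5 v 5 AUC difference: 31%, or 27% if decline correlates 0.3 with baseline. Estimating the slope in 18 patients gives back about 4%.

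For change from baseline the point reduces to a caution about late visits, where the floor at 0 makes a higher start look like a larger fall. No case for modelling it visit by visit follows. The gain is in precision and in fair reading of a secondary, exploratory result. It does not make the trial informative about viral efficacy.

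**What to change.** In protocol section 7.4.4 and SAP section 9, beside the descriptive AUC table for the final report, specify one supportive linear model: viral AUC on treatment group (four levels) and pre-dose log10 titer, with one common slope. Report baseline-adjusted group means and differences from placebo with 95% confidence intervals, labelled exploratory. Fix the specification before unblinding.

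Do not add models of change from baseline at each visit. Show each group's baseline titer beside those summaries so that an imbalance is read together with the change.

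The cost is one model and one table from data already scheduled, with no new samples, visits or patients. The downside is an assumed roughly linear, common baseline effect fitted with about 13 residual degrees of freedom. For that reason the model should sit alongside the unadjusted summary and not replace it.

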### **7.4.5 Efficacy Analysis**

The secondary efficacy endpoints will be analyzed on ITT set and will be summarized by the cohort of CT-P59 groups and pooling of placebo group using descriptive statistics or frequency tables.

#### **7.4.6 Pharmacokinetic Analysis**

All PK analyses will be conducted in the PK Set. The PK parameters of CT-P59 will be analyzed using noncompartmental methods based on the actual sampling time points. All parameters will be calculated using Phoenix WinNonlin (Pharsight, St Louis, Missouri, USA).

Pharmacokinetic parameters of  $AUC_{0-\infty}$ ,  $AUC_{0-\infty} / \text{Dose}$ ,  $AUC_{0-\text{last}}$ ,  $AUC_{0-\text{last}}/\text{Dose}$ ,  $C_{\max}$ ,  $C_{\max} / \text{Dose}$ ,  $T_{\max}$ ,  $t_{1/2}$ ,  $\%AUC_{\text{ext}}$ ,  $\lambda_z$ ,  $CL$ , and  $V_z$  will be presented in data listings and summarized by the cohort of CT-P59 groups at each scheduled visit using descriptive statistics.

Serum concentration data will be presented in data listings and summarized by the cohort of CT-P59 groups at each scheduled visit using descriptive statistics.

#### **7.5 Interim Analysis**

No formal interim analysis will be performed in this study. The Sponsor plans to prepare two CSRs ([Section 9.7](#)).

#### **7.6 Data Quality Assurance**

This study will be conducted according to the ICH E6(R2) risk and quality processes described in the applicable procedural documents. The quality management approach to be implemented in this study will be documented and will comply with the current ICH GCP guidelines on quality and risk management.

Steps to be taken to ensure the accuracy and reliability of data include the selection of qualified Investigators and appropriate study center, review of protocol procedures with the Investigator and associated staff prior to the study, periodic monitoring visits by the Sponsor or its designee, and direct transmission of clinical laboratory data from central and/or local laboratories into the clinical database. The data will be collected via Electronic Data Capture (EDC) using eCRFs. The study center will be responsible for data entry into the EDC system. The eCRF will be reviewed for accuracy and completeness by the monitor during on-site monitoring visits and after their return to the Sponsor or its designee. In the event of discrepant data, the Sponsor will request data clarification from the study center, which the study center will resolve electronically in the EDC system. The Sponsor will be responsible for the data management of this study, including quality checking of the data.

Central laboratory data will be sent directly to the Sponsor using their standard procedures to handle and process the electronic transfer of these data. Quality assurance staff from the Sponsor or its designee may visit the study center to carry out an audit of the study in compliance with

regulatory guidelines and company policy. Such audits will require access to all study records, including source documents, for inspection and comparison with the eCRF. Patient privacy must, however, be respected. Sufficient prior notice will be provided to allow the Investigator to prepare properly for the audit.

Similar auditing procedures may also be conducted by agents of any regulatory body reviewing the results of this study in support of a licensing application. The Investigator should immediately notify the Sponsor or its designee if he or she has been contacted by a regulatory agency concerning an upcoming inspection.

## **8 Investigator's Obligations**

The following administrative items are meant to guide the Investigator in the conduct of the study but may be subject to changed based on industry and government SOPs, working practice documents, or guidelines. Changes will be reported to the IEC but will not result in a protocol amendment.

### **8.1 Confidentiality**

All laboratory specimens, evaluation forms, reports, and other records will be identified in a manner designed to maintain patient confidentiality. All records will be kept in a secure storage area with limited access. Clinical information will not be disclosed without the written permission of the patient (or the patient's legal guardian), except as necessary for monitoring and auditing by the Sponsor, its designee, the regulatory authorities or the IEC.

The Investigator, all employees, and coworkers involved with this study may not disclose or use for any purpose other than performance of the study, any data, record, or other unpublished, confidential information disclosed to those individuals for the purpose of the study. Prior written agreement from the Sponsor or its designee must be obtained for the disclosure of any said confidential information to other parties.

### **8.2 Independent Ethics Committee**

Regulations and ICH guidelines require that approval be obtained from an IEC before participation of human patients in research studies. Before study onset; the protocol, informed consent, advertisements to be used for the recruitment of study patients, and any other written information regarding this study to be provided to the patient or the patient's legal guardian, must be approved by the IEC. Documentation of all IEC approvals and of the IEC compliance with [ICH harmonised tripartite guideline E6\(R2\)](#): GCP will be maintained by the study center and will be available for review by the Sponsor or its designee.

All IEC approvals should be signed by the IEC chairman or designee and must identify the IEC name and address, the clinical protocol by title or protocol number or both, and the data approval or a favorable opinion was granted.

The Investigator is responsible for providing written summaries of the progress and status of the study at intervals not exceeding 1 year or otherwise specified by the IEC. The Investigator must promptly supply the Sponsor or its designee, the IEC, and, where applicable, the institution,

with written reports on any changes significantly affecting the conduct of the study or increasing risk to patients.

### **8.3 Patient Information and Consent**

A written informed consent in compliance with ICH E6(R2) guidelines will be obtained from each patient before entering the study or performing any unusual or nonroutine procedure that involves risk to the patient. An informed consent template may be provided by the Sponsor to the study center. If any institution-specific modifications to study-related procedures are proposed or made by the study center, the consent should be reviewed by the Sponsor or its designee or both before IEC submission. Once reviewed, the consent will be submitted by the Investigator to his or her IEC for review and approval before the start of the study. If the ICF is revised during the course of the study, all active participating patients must sign the revised form in case new information becomes available that may be relevant to the patient's willingness to continue participation in the clinical study.

Before recruitment and enrollment, each prospective patient/legal guardian will be given a full explanation of the study and be allowed to read the approved ICF. Once the Investigator is assured that the patient/legal guardian understands the implications of participating in the study, the patient/legal guardian will be asked to give consent to participate in the study by signing the ICF.

In addition to the standard requirements that physicians are currently obliged to observe when providing information, the following points must also be covered:

- A description of the objectives of the study and how it will be organized
- The type of treatment
- Any potential negative effects attributable to the study drug
- The freedom to ask for further information at any time
- The patient's right to withdraw from the clinical study at any time without giving reason and without jeopardizing the patient's further course of medical treatment
- The existence of patient insurance coverage and a summary of what is included in this coverage
- Adequate time and opportunity to satisfy questions will be given to the patients

The Investigator will be supplied with an adequate number of ICFs to be used. The forms will be signed and dated by both the Investigator or Sub-Investigator and the patient's legal representatives (according to the local regulations) before the beginning of the study. The Investigator shall retain the signed original ICF(s) and give a copy of the signed original form to the patient or legal guardian.

To ensure medical confidentiality and data protection, the signed ICFs will be stored in the Investigator's study file. The Investigator will allow inspection of the forms by authorized representatives of the Sponsor, IEC members, and regulatory authorities. The Investigator will confirm, by signing and dating the eCRFs, that informed consent has been obtained.

## **8.4 Study Reporting Requirements**

By participating in this study, the Principal Investigator or Sub-Investigator agrees to submit reports of SAEs according to the timeline and method outlined in [Section 6.1.1.1.7](#). In addition, the Principal Investigator or Sub-Investigator agrees to submit annual report to his or her IEC as appropriate.

## **8.5 Financial Disclosure and Obligations**

CELLTRION, Inc. is the Sponsor of the study and is funding the study. All financial details are provided in the separate contracts between the institution, Investigator, and CRO. The Sponsor maintains appropriate insurance coverage for clinical studies and will follow applicable local compensation laws. The Sponsor will indemnify all Investigators participating in this study against future claims by study patients; the terms of this will be detailed within a separate letter of indemnification. The indemnity will only apply where all study procedures have been carried out according to this protocol.

The Investigator is required to take out liability insurance for all patients included in the study as required by local law and/or regulations and/or ICH GCP, whichever is applicable.

The Investigator and the Sponsor will sign a clinical study agreement before the start of the study. The agreement will outline overall Sponsor and Investigator responsibilities in relation to the study. Financial remuneration will cover the costs based on the calculated expenses of performing the study assessments in accordance with the protocol and the specified terms of payment will be described in the contract.

Investigators are required to provide financial disclosure information to allow the Sponsor to submit the complete and accurate certification or disclosure statements per regional

requirements. In addition, the Investigator must provide to the Sponsor a commitment to promptly update this information if any relevant changes occur during the course of the investigation and for 1 year following the completion of the study.

Neither the Sponsor nor its designee is financially responsible for further testing or treatment or any medical condition that may be detected during the Screening process. In addition, in the absence of specific arrangements, neither the Sponsor nor its designee is financially responsible for further treatment of the patient's pre-existing disease prior to study participation (Screening).

The Sponsor undertakes to compensate the patient for injuries which are considered, on the balance of probabilities, to have arisen as a result of their participation in the trial.

